**Table 12: Source data in TONIC**

| Data                          | Source  |
|-------------------------------|---|
| Participant Reported Outcomes | The original record of questionnaire completion is the source data. Questionnaires can be completed by participants electronically or on paper.
If completed electronically the electronic record will be the source data, held on BCTU servers as part of the electronically-enabled questionnaire completion. If completed on paper, the paper record will be the source data and will be entered onto the trial EDC system. |
| Lab results                   | The original lab report (which may be electronic) is the source and will be kept and maintained, in line with normal local practice. Information will be transcribed onto CRFs.   |
| Blood pressure                | The routine clinic blood pressures at various time points will be available from the medical notes/electronic participant record system, which will be kept and maintained in line with normal  |

|                       |   |
|-----------------------|---|
|                       | local practice. The medical notes/electronic participant record system is the source and will be transcribed onto CRFs.   |
| Clinical event data   | The original clinical annotation is the source document. This may be found on clinical correspondence, or electronic or paper participant records. Clinical events reported by the participant, either in or out of clinic (e.g., phone calls), must be documented in the source documents. |
| Health economics data | Data will be completed directly on to the CRF by the participant and this will constitute the source data. The CRF is source data.  |
| Recruitment           | The original record of the randomisation is the source. It is held on BCTU servers as part of the EDC system.   |
| Withdrawal            | Where a participant expresses a wish to withdraw, the conversation must be recorded in the source documents.  |

## 11.2 Case Report Form (CRF) completion

eCRFs should be submitted directly into the TONIC trial system for each individual subject. Staff delegated to complete eCRFs will be trained to adhere to the eCRF completion guidelines. Worksheets will be provided to sites to aid with data collection only and will not form part of the eCRF.

The eCRFs will include (but will NOT be limited to) the forms detailed below.

**Table 13: Case report forms in TONIC**

| Form Name            | Schedule for submission  |
|----------------------|--|
| Screening Log        | When a participant is being considered for approach to participate in the TONIC Trial. |
| Informed Consent     | Prior to randomisation   |
| Randomisation Form   | At the point of randomisation  |
| Baseline Data Form   | As soon as possible after consent  |
| Patient Contact Form | As soon as possible after consent  |
| Index Surgery Form   | Completed during hospital stay for index surgery                                       |

|  |   |
|--|---|
| Follow-up CRFs including participant reported outcome measures | As soon as possible after each follow-up assessment time point  |
| Serious Adverse Event Form                                     | If expedited: within 24 hours of site research team becoming aware of event
If non-expedited: in accordance with section 10. |
| Pregnancy Notification Form                                    | As soon as possible after becoming aware of participant's pregnancy   |
| Pregnancy Outcome Form   | As soon as possible after outcome of pregnancy and/or birth of the child  |
| Trial Exit/Change of status CRF                                | At the point of becoming aware of withdrawal/change of status or death  |

An eCRF should be completed for each individual participant.

In all cases, it remains the responsibility of the PI to ensure that the electronic CRF (eCRF) has been completed correctly and that the data is accurate. This will be evidenced by the electronic signature of the PI, or delegate(s). The Site Signature & Delegation Log will identify all those personnel with responsibilities for data collection. The delegated staff completing the eCRF should ensure the accuracy, completeness and timeliness of the data reported. This will be evidenced by signing and dating the eCRF.

Data reported on each eCRF will be consistent with the source data and any discrepancies will be explained. All missing and ambiguous data will be queried. Staff delegated to complete CRFs will be trained to adhere to the TONIC trial specific working instructions on eCRF completion.

The following guidance applies to data and partial data:

- Time format – all times should be in accordance with the 24hr clock
- Rounding conventions – rounding should be to the nearest significant number according to the CRF: If the number you are rounding is followed by 5, 6, 7, 8, or 9, round the number up. **Example:** 3.8 rounded to the nearest whole number is 4. If the number you are rounding is followed by 1, 2, 3 or 4, round the number down.  
**Example:** 3.4 rounded to the nearest whole number is 3
- Trial-specific interpretation of data fields – where guidance is needed additional information will be supplied

---

- Entry requirements for concomitant medications (generic or brand names) – generic names should be used where possible
- Missing/incomplete data – should be clearly indicated – all blank fields will be queried by the Trial Office
- Repeat laboratory tests – the data used to inform clinical decisions should always be supplied. If a test is repeated it is either to confirm or clarify a previous reading. Confirmatory tests should use the original test values.
- Protocol and GCP non-compliances should be reported to the Trial Office on discovery.

The eCRFs will be considered “complete” once all data fields have been either completed unambiguously or it has been made explicit that the data is unobtainable.

### **11.3 Participant completed questionnaires**

A list of all participant completed forms can be found in Table 14.

**Table 14: A list of participant completed questionnaires**

| Name of questionnaires                     |
|--|
| EQ-5D-5L                                   |
| Pro-DiGI gastrointestinal recovery measure |
| Quality of Recovery-15 questionnaire       |
| Health Resource Usage questionnaire        |
| Patient Satisfaction Visual Analogue Score |

Participant completed questionnaires can be completed online or on paper. Questionnaires should generally be completed by the participant alone, however physical assistance in completing the form can be given by the research staff or the participant’s friends and relatives where appropriate. In such circumstances, questions are to be read to the participant verbatim and responses must not be led by the person assisting with the form completion. This requirement must be made clear when the participant’s friends and relatives are providing the assistance. Participants should be encouraged to respond to all questions but can refuse to answer any, or all, of the questions should they wish to by selecting ‘Prefer not to answer’.

## 11.4 Data management

Processes will be employed to facilitate the accuracy and completeness of the data included in the final report. These processes will be detailed in the trial specific Data Management Plan (DMP) and include the processes of data entry, data queries on trial data.

Data entry will be completed by the sites via a BCTU REDCap EDC system. The data capture system will conduct automatic range checks for specific data values to ensure high levels of data quality. Queries will be raised via the trial EDC system, with the expectation that these queries will be completed by the site within 30 days of receipt. Overdue data entry and data queries will be requested on a monthly basis.

Trial EDC system access will be controlled by usernames and passwords, and any changes to data will require the user to be logged in using their username and password. Log-in details must not be shared with other individuals and under no circumstances should individual's access the system using another person's login details. Access within the system is restricted to the functionality and data that are appropriate for the individual's role in the trial.

## 11.5 Self-evident corrections

No self-evident corrections will be permitted.

## 11.6 Data security

UoB has policies in place, which are designed to protect the security, accuracy, integrity and confidentiality of Personal Data. The trial will be registered with the Data Protection Officer at UoB and will hold data in accordance with the Data Protection Act (2018 and subsequent amendments). The Trial Office has arrangements in place for the secure storage and processing of the trial data which comply with UoB policies.

The Trial EDC System incorporates the following security countermeasures:

- **Physical security measures:** restricted access to the building, supervised onsite repairs and storages of back-up tapes/disks are stored in a fire-proof safe.
- **Logical measures for access control and privilege management:** including restricted accessibility, access controlled servers, separate controls of non-identifiable data.
- **Network security measures:** including site firewalls, antivirus software and separate secure network protected hosting.
- **System management:** the system will be developed by the Programming Team at the Trial Office, and will be implemented and maintained by the Programming Team

- **System design:** the data collection system will comprise of a database and a data entry application with firewalls, restricted access, encryption and role based security controls.
- **Operational processes:** the data will be processed and stored within BCTU.
- **System audit:** The system will benefit from the following internal/external audit arrangements:
  - Internal audit of the system
  - Periodic IT risk assessment
- **Data Protection Registration:** UoB's Data Protection Registration number is Z6195856.

Data will be shared with the University of Sheffield to enable statistical and health economic analyses, where it will be held within an access restricted folder within the University of Sheffield's file store. All servers are virtual servers hosted within the University of Sheffield's virtual server estate. The system is hosted in data centres located in Sheffield, UK that are owned and operated by the University of Sheffield's IT Services department.

## **11.7 Archiving**

All records created by following trial procedures and all documents listed in guidance relating to the conduct of the trial must be retained and archived for the specified period.

The TMF is normally composed of a sponsor file, held by the sponsor organisation, and an ISF, held by the site investigator. Documents are archived following regulatory requirements and local procedures.

Retained data should still be accurate, accessible and stored securely and confidentially.

It is the responsibility of the PI to ensure all essential trial documentation and source documents (e.g., signed ICFs, ISFs, participants' hospital notes, copies of worksheets) at their site are securely retained for the contractual period. Archiving will be authorised by BCTU on behalf of UoB following submission of the end of trial report. No documents should be destroyed without prior approval from the BCTU Director or their delegate.

The TMF will be stored at BCTU for at least 3 years after the end of the trial. Long-term offsite data archiving facilities will be considered for storage after this time; data will be stored securely and confidentially for at least 10 years. BCTU has standard processes for both hard copy and computer database legacy archiving. No documents will be destroyed without prior approval from the TONIC Trial Office.

## 12. QUALITY CONTROL AND QUALITY ASSURANCE

### 12.1 Site set-up and initiation

All PIs will be asked to sign the necessary agreements including a TONIC Site Signature and Delegation log between the PI and the Trial Office and supply a current CV and GCP certificate. All members of the site research team are required to sign the Site Signature and Delegation Log, which details which tasks have been delegated to them by the PI. The Site Signature and Delegation Log should be kept up to date by the PI. It is the PI's responsibility to inform the Trial Office of any changes in the site research team.

Prior to commencing recruitment, each recruiting site will undergo a process of site initiation, either a meeting or a tele/video conference, at which key members of the site research team are required to attend, covering aspects of the trial design, protocol procedures, adverse event reporting, collection and reporting of data and record keeping. Sites will be provided with an ISF containing essential documentation, instructions, and other documentation required for the conduct of the trial. The PI or delegate is required to keep the ISF up to date throughout the trial.

### 12.2 Monitoring

The central and on-site monitoring requirements for this trial have been developed in conjunction with the trial specific risk assessment and are documented in the trial specific monitoring plan.

#### 12.2.1 On-site monitoring

All sites will be monitored in accordance with the trial risk assessment and monitoring plan. Any monitoring activities will be reported to the Trial Office and any issues noted will be followed up to resolution. Additional on-site monitoring visits may be triggered. PIs and site research teams will allow the TONIC trial staff access to source documents as requested. The monitoring will be conducted by BCTU/UoB staff. Any issues noted will be followed up to resolution.

#### 12.2.2 Central monitoring

The Trial Office will check received ICFs and eCRFs for compliance with the protocol, data consistency, missing data and timing at a frequency and intensity determined by the DMP. Sites will be sent queries raised via the trial EDC system requesting missing data or clarification of inconsistencies or discrepancies.

## **12.3 Audit and inspection**

The Investigator will permit trial-related monitoring, audits, ethical review, and regulatory inspection(s) at their site and provide direct access to source data/documents. The investigator will comply with these visits and any required follow-up. Sites are also requested to notify the Trial Office of any relevant inspections or local audits.

## **12.4 Notification of Serious Breaches**

The sponsor is responsible for notifying the REC of any serious breach of the conditions and principles of GCP in connection with that trial or of the protocol relating to that trial. Sites are therefore requested to notify the TONIC Trial Office of any suspected trial-related serious breach of GCP and/or the trial protocol as soon as they become aware of them. Where the TONIC Trial Office is investigating whether or not a serious breach has occurred, sites are also requested to co-operate with the Trial Office in providing sufficient information to report the breach to the REC where required and in undertaking any corrective and/or preventive action.

Sites may be suspended from further recruitment in the event of serious and persistent non-compliance with the protocol and/or GCP, and/or poor recruitment.

## **13. END OF TRIAL DEFINITION**

The end of trial will be the date of the last data capture including resolution of data queries. This will allow sufficient time for the completion of protocol procedures, data collection and input and data cleaning. The Trial Office will notify the REC and the Sponsor within 90 days of the end of trial. Where the trial has terminated early, the Trial Office will notify the REC within 15 days of the end of trial. The Trial Office will provide the REC and the Sponsor with a summary of the clinical trial report within 12 months of the end of trial.

## 14. STATISTICAL CONSIDERATIONS

### 14.1 Sample size

The CCI uses a combination of frequency and weighting to score complications along the CDC framework[36]. Previous literature has demonstrated the standard deviation of this measure to be ~27 for this population[18]. Perinel et al demonstrated an 8-point difference in CCI following early TPN in the elective setting, which corresponded to a 12% reduction in grade III-V complications[43]. Based on the increased acuity and complexity of this patient group, we believe a 6 point reduction in CCI to be a feasible and relevant effect size. A 6-point difference is equivalent to downgrading a class III complication to a class II complication[29]. Allowing for up to 5% attrition, 90% power, 5% two-sided significance threshold, a sample size of 449 participants in each arm is needed (total 898).

### 14.2 Analysis of outcomes

A separate Statistical Analysis Plan will be produced and will provide a more comprehensive description of the planned statistical analyses. There are no planned interim analyses. A brief outline of the planned analyses is given below. The results of the analysis will be reported and presented according to CONSORT 2010 guidance[45].

The primary comparison groups will be composed of those randomised to early PN versus those randomised to standard nutritional care according to the intention to treat principle, i.e., all participants will be analysed in the intervention group to which they were randomised irrespective of adherence to randomised intervention or protocol deviations.

The estimand framework will be used to clarify the interpretation of the treatment effect for the primary outcome[46]. The framework covers analyses' key points: analysis population, the treatments compared, primary endpoint, summary measure, and the handling of intercurrent events, and is covered in greater detail in the Statistical Analysis Plan.

**Table 15: Brief description of the TONIC Estimand**

| Estimand Attribute | Primary Analysis  |
|--------------------|---|
| Population         | Patients aged 18 or over undergoing NELA eligible emergency laparotomy  |
| Treatments         | Early PN (defined for this study as commencement of PN within 48 hours of laparotomy) compared to standard nutritional care which can include a combination of oral nutritional |

|                                 |   |
|---------------------------------|---|
|                                 | supplements, nasoenteric feed, or no additional nutritional support.  |
| Primary Endpoint                | CCI Score of in hospital complications measured at point of hospital discharge  |
| Summary Measure                 | Mean difference with 95% confidence interval  |
| Handling of intercurrent events | 
 
The analysis will be according to a 'treatment policy' estimand strategy, meaning treatment non-compliance or treatment switching will be ignored in the primary analysis and patients will be analysed as randomised. A secondary analysis with complier-adjusted causal effect (CACE) will be undertaken to estimate the maximal achievable benefit if received as planned (principal stratum strategy). This will be explored further in the Statistical Analysis Plan.
 
Death post-operation is reflected in the primary outcome (CCI) as a score of 100.
 
 |

For all outcomes, appropriate summary statistics and differences between groups, (e.g., mean differences, ORs) will be presented, with 95% confidence intervals and p-values from two-sided tests also provided. Where possible intervention effects will be adjusted for the minimisation variables listed in Section 6. No adjustment for multiple comparisons will be made.

Continuous variables will be summarised by mean, median, minimum, and maximum value alongside the standard deviation and inter-quartile range (IQR). Categorical variables will be summaries by group with proportions and numbers, in each treatment arm and overall.

### 14.2.1 Primary outcome(s)

The Comprehensive Complication Index ranges from 0 (no complications) to 100 (death). Previous studies suggest a median CCI score of 21 (IQR 0-29)[8]. Data required to calculate this are all recorded complications, associated with a CDC. Full details of the CCI scoring will be given in the Statistical Analysis Plan (SAP).

The primary analysis will be conducted using linear regression with bootstrapped confidence intervals to account for the non-normal distribution, with covariates comprising randomised arm, site, plus minimisation factors. The treatment difference will be reported as a mean difference with 95% confidence interval. The p-value relating to the intervention group parameter as generated by the model will be presented. The primary analyses will be intention to treat.

As some treatment withdrawal or switchover is expected, the primary outcome will also be analysed using a CACE analysis, in order to estimate the maximal achievable benefit of nutritional supplementation if taken as planned. Further details including per-protocol definition of treatment adherence will be documented in the SAP.

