## **6.5 Randomisation method**

Participants will be randomised at the level of the individual in a 1:1 ratio to either early administration of PN or standard care via a central secure web-based randomisation system available 24 hours/day at the BCTU. A minimisation algorithm will be used within the randomisation system to ensure balance in the intervention allocations over the following variables:

- NELA risk (<5 OR ≥5%) [33]
- Nutrition Risk Score (<3 OR ≥3) [34]
- Recruiting site (hospital name).

To avoid the possibility of the intervention allocation becoming predictable, a random element will be included in the algorithm. Full details of the randomisation specification will be stored in a confidential document at BCTU.

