### Baseline (Pre-randomisation)

Once informed consent has been obtained, patients will have key demographic data recorded. The research team will enter the data items needed to determine the Nutrition Risk Screening (NRS-2002) score on to the online EDC system, which will then calculate the score. Data collected as part of routine care includes the MUST, medical history, and the NELA mortality risk score. The patient will also complete an EQ-5D-5L questionnaire. The participant is to be guided to complete the questions on the EQ-5D-5L based on their health and wellbeing prior to the start of the episode that requires surgery. If the participant is not able to complete this then EQ-5D-5L will not be recorded.

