#### **14.2.2 Secondary outcomes**

Secondary outcomes will be analysed for the intention to treat analysis population. Binary outcomes will be analysed using logistic regression with covariates of minimisation factors. The treatment difference will be reported as an OR with corresponding 95% confidence interval. Continuous secondary outcomes such as questionnaires and patient-reported outcome measures (PROMs) will be analysed analogously to the primary outcome using linear regression (95% confidence intervals will not be bootstrapped). Length of hospital stay will be log-transformed analysed using linear regression: summaries on mean fold difference and absolute difference will be presented.

For safety outcomes and adverse events, the following summaries will be presented: the number and percentages of patients reporting SAEs in each arm. In addition, the number of participants requiring further interventions or revisions will be summarised descriptively.

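### As the protocol reads, the primary model adjusts for two-level cuts of scores already held in full, and its confidence interval and p-value come from different procedures

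*Protocol*

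**What the plan says.** - **Primary model (Section 14.2.1).** The analysis is "linear regression with bootstrapped confidence intervals to account for the non-normal distribution, with covariates comprising randomised arm, site, plus minimisation factors". The next statement on inference is: "The p-value relating to the intervention group parameter as generated by the model will be presented". No bootstrap p-value is named, nor any rule for a conflict between the two.
- **Covariates (Sections 14.2 and 6.5).** The text after Table 15 ties adjustment, where possible, to the minimisation variables of Section 6. Section 6.5 lists these as NELA risk in two levels (the entry begins "NELA risk (<5 OR ≥5", in per cent), Nutrition Risk Score below 3 or at least 3, and site.
- **Baseline data (Section 9).** The items for NRS-2002 are entered and the system calculates the score. The NELA mortality risk score is also collected. On quality of life: "The patient will also complete an EQ-5D-5L questionnaire". It refers to health before the surgical episode and is left unrecorded if the patient cannot complete it.
- **Secondary outcomes (Section 14.2.2).** Continuous outcomes, including patient-reported measures, "will be analysed analogously to the primary outcome using linear regression", but without bootstrapping. No baseline value is named as a covariate.
- **Sample size (Section 14.1).** "Allowing for up to 5% attrition, 90% power", with a "5% two-sided significance threshold", a 6-point difference and an SD of about 27, gives 449 per arm. The calculation takes no credit for covariates.

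**The concern.** There are two separate issues.

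The first is efficiency. Death scores 100 on the CCI, so predicted mortality is an obvious prognostic covariate. A cut at 5% treats a patient at 6% risk like one at 40%. The trial already holds the finer information, so coarse coding saves nothing. The same applies to leaving baseline EQ-5D-5L out of the model for later EQ-5D-5L.

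The second is coherence. The protocol bootstraps the interval because the outcome is not normal, then reports a p-value from the model whose approximation was the reason for bootstrapping. Each is defensible alone. Together they can give opposite answers at the 5% level, and a choice made after seeing the data would be open to criticism.

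**Working it through.** **1. Reproduce the stated sample size.** Inputs from Section 14.1: difference 6, SD 27, two-sided 5%, power 90%, attrition 5%.

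n per arm = 2 × 27² × (1.960 + 1.282)² / 6² ≈ 426. Then 426 / 0.95 = 448.4, rounded up to 449, or 898 in total. This matches. Power at 426 analysed per arm is 0.900 with no covariate effect, so any gain from adjustment comes on top of the plan.

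**2. What a two-level cut keeps.** For a normally distributed covariate with a linear effect, cutting it so that a share p falls on one side keeps the fraction φ(z_p)² / [p(1 − p)] of its R²:

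- 50/50 split: 0.637
- 30/70 split: 0.576
- 20/80 split: 0.490

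**3. Value of the continuous scores.** With R²cut = R² × fraction kept:

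- participants' worth = 852 × [1 − (1 − R²)/(1 − R²cut)]
- power is that of a two-mean comparison with SD = 27 × √(1 − R²) or 27 × √(1 − R²cut)

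Example at R² = 0.10, 50/50 split: R²cut = 0.064, the variance ratio is 0.90/0.936 = 0.961, and 852 × 0.039 ≈ 33.

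| Assumed R² of the scores | Power, continuous | Power, cut (20/80 to 50/50) | Worth, of 852 participants |
|---|---|---|---|
| 0.02 | 0.906 | 0.903–0.904 | 6–9 |
| 0.05 | 0.914 | 0.907–0.909 | 16–22 |
| 0.10 | 0.928 | 0.914–0.918 | 33–46 |
| 0.20 | 0.952 | 0.927–0.935 | 71–96 |
| 0.30 | 0.972 | 0.940–0.950 | 115–153 |

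The protocol gives neither R² nor the split. Taking R² of 0.05 to 0.20 as a plausible band, the gain is 16 to 96 participants and about 0.5 to 2.5 points of power.

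**4. Baseline EQ-5D-5L.** Adjusting for a baseline value with correlation r removes a share r² of the outcome variance. For an assumed r of 0.3 to 0.6 this is 0.3² = 9% to 0.6² = 36%. The protocol gives no correlation. Because the baseline is recalled pre-illness health, the lower end should not be ruled out.

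**5. Interval against p-value.** Trials of 852 participants were simulated with 25 sites, two binary covariates and a skewed 0–100 outcome (8% at 100, SD about 27.6) chosen to resemble the figures in Sections 14.1 and 14.2.1. The ordinary regression p-value was compared with a 95% percentile bootstrap interval (500 resamples).

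| Mean simulated difference | p < 0.05 | Interval excludes 0 | Disagree |
|---|---|---|---|
| about 0 (null) | 4.2% | 5.0% | 1.2% |
| about 3.4 points | 46.5% | 47.3% | 3.3% |
| about 5.2 points | 85.8% | 86.3% | 2.5% |

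A second set of simulations gave 0.8% to 3.4% with 1,000 resamples and 0.3% to 1.5% with 4,000, so part of the disagreement is resampling noise. Both methods centre on the same estimate and reject at nearly the same rate, so conflicts arise where p is close to 0.05.

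**The case against.** The strongest reply is that the protocol calls its analysis section a brief outline and defers detail to a separate SAP. It never states how the scores are coded. Section 6.5 gives cuts for balancing allocation, and the SAP could enter the scores as continuous. That stands: a reader might infer that the protocol commits to yes/no covariates only, but this is the natural reading, not an explicit statement. The same holds for EQ-5D-5L, where an analogous analysis does not exclude a baseline covariate.

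A reader might also infer that the trial is biased or underpowered by this choice. It is not. Adjusting for minimisation factors as used in allocation is valid, and the 90% power was computed without covariates.

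On inference, a reader might conclude that the p-value is invalid or that the trial could end without a primary result. The simulated rejection rates do not support the first. Against the second, Table 15 names the mean difference with its 95% confidence interval as the summary measure. It can further be argued that a p-value generated by the model might come from the bootstrapped fit. The wording does not exclude this, but nor does it say so, and the regression's own test is the plainer reading.

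What remains is that the protocol fixes the covariate list and the source of the p-value in its own text. Both can be improved at almost no cost.

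**Conclusion.** The point holds as an inexpensive improvement to a stated analysis, not as an error that invalidates it.

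- **Covariates.** The loss is modest precision, about 16 to 96 of 852 participants. It rests on an assumed R² of 0.05 to 0.20, a normal covariate with a linear effect, splits between 50/50 and 20/80, and the two-level reading being correct.
- **EQ-5D-5L.** The loss concerns a secondary outcome, and its size rests wholly on an assumed correlation.
- **Interval and p-value.** The mismatch is in the text. It would change the significance verdict in roughly 1% to 3% of trials, fewer with many resamples, under an assumed outcome distribution and a percentile bootstrap. Neither method is materially miscalibrated. The defect is that no deciding rule is set in advance.

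**What to change.** 1. State that the primary model includes NELA risk (for example on the logit scale) and NRS-2002 as continuous covariates, plus site. The two-level versions may stay in as well. This also keeps the adjustment independent of the NRS cut-off, which is 3 in Section 6.5 but 4 in Section 14.2.3, where it is described as a minimisation variable. Those two sections need reconciling in any case.
2. Take the primary confidence interval and p-value from the same procedure. If that is the bootstrap, fix its type and number of resamples in advance (for example 10,000, stratified by arm).
3. Add baseline EQ-5D-5L as a covariate for the EQ-5D-5L outcomes, with mean imputation where it was not recorded.

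The cost is wording in the protocol or SAP and slightly more analysis work, with no new data. The one added assumption is the functional form of the scores. In a randomised comparison, a poor fit there costs some of the precision gain and does not bias the treatment effect. The change should be made before anyone sees outcome data by arm.
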